13.5 SOLRIAMFETOL INFORMATION

13.5.1 RISK ASSESSMENT

Potential safety risks associated with the use of solriamfetol include serious psychiatric events, increases in blood pressure and heart rate, and potential for abuse. Psychiatric events occur more commonly in the narcolepsy population; participants with narcolepsy and severe psychiatric disorders will be excluded from this study per the Platform Protocol exclusion criteria (Section 5.2). Participants at risk for cardiovascular events are excluded from Appendix A. Nonclinical and clinical data that show the potential for abuse with solriamfetol are low.

Clinical trials in patients with narcolepsy and OSA indicate that the following AEs occur at a higher percentage in those who receive 75 or 150 mg of solriamfetol versus placebo: headache (1% to 9%), nausea (0% to 4%), decreased appetite (6% to 7%), anxiety (2% to 6%), and insomnia (0% to 1%).⁵⁹

13.5.2 FORMULATION, APPEARANCE, PACKAGING, AND LABELING

Solriamfetol is a small molecule with the chemical name of (R)-2-amino-3-phenylpropylcarbamate hydrochloride. It will be a blue tablet.

The placebo tablet will be tooled to look similar to the solriamfetol tablet, but it will not contain the active ingredient.

Solriamfetol and the placebo will be packaged in high-density polyethylene bottles with a child-resistant screw cap. All packaging will be labeled to indicate that the products are for investigational use.⁶⁰

13.5.3 DRUG DISPENSING, STORAGE, AND STABILITY

Unblinded study personnel will manage solriamfetol and placebo disbursement to maintain blinding among participants and blinded study personnel, including site investigators.

Solriamfetol and the placebo should be stored at 20 °C to 25 °C (68 °F to 77 °F) with excursions permitted between 15 °C to 30 °C (59 °F to 89 °F). Do not freeze the product. Both active solriamfetol and the placebo are stable at these temperatures for 60 months.⁶⁰

13.5.4 DOSING AND ADMINISTRATION

Solriamfetol dosing will total 10 weeks, including 3 weeks for titration and 7 weeks of maintenance.

Over the first 3 weeks, solriamfetol will be titrated starting at 75 mg (1 tablet) daily in the morning. Every 5 days (± 2 days), the study team will call participants according to the following schedule.

- Day 5: participants will be contacted to discuss symptoms but no titration will occur.
- Day 10: participants may increase to 150 mg (2 tablets) daily in the morning according to the titration guidance in the MOP. The goal of titration is for participants to take the highest dose permitted by symptoms.
- Day 15: participants may titrate or maintain their dose depending on their symptoms and tolerance to solriamfetol.
- Day 20: participants may titrate or maintain their dose depending on their symptoms and tolerance to solriamfetol. The dose selected or maintained at this day will be the dose for the following 7 weeks of maintenance.

Placebo dosing will follow the solriamfetol dosing scheme and goal.

Dosing will follow this schedule in the absence of adverse reactions deemed likely attributable to treatment by a study physician, with special attention to headache, nausea, decreased appetite, insomnia, anxiety, or BP exceeding the threshold described in the study exclusion criteria. See the MOP for detailed guidance. In the case of adverse reactions, the dose may be reduced to the most recent prior dose at weekly intervals until adverse symptoms are alleviated or the medication is discontinued.

13.5.5 RATIONALE FOR SELECTION OF DOSE

The proposed doses and the schedule of dose escalation are consistent with currently approved FDA labeling for solriamfetol for other disorders of excessive daytime sleepiness.⁶⁰

13.6 EVENTS OF SPECIAL INTEREST

The following ESIs will be collected for Appendix A:

- Hypertension
 - Rhinitis Pharyngitis
- Headache
- Rash
- DiarrheaNausea/vom
- Nausea/vomiting
 Backpain
- Psychiatric event
- Back pain

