9.1.2 COLLECTION PERIOD OF AE AND SAE INFORMATION

Safety event collection will occur at the pre-specified study visits but all participants will be instructed to self-report concerns by calling the site.
Serious adverse events (SAEs), UADEs, or ESIs (per appendix) will be extracted by site personnel from the participant's medical record if the participant seeks medical care or if hospitalization occurs, each of which notifies the site to conduct follow-up.

Medical occurrences that begin before the first invasive study procedure (blood collection or nasal swab), but after obtaining informed consent, will not be considered an AE. The medical occurrence or condition will be captured on the Medical History electronic case report form (eCRF).

Non-serious AEs may be reported by the participant, but will not be collected into the study database as an AE or further assessed by the site or study personnel. Non-serious AEs that result in study intervention discontinuation will be identified as the reason for study intervention discontinuation in the study database and reported separately as an AE, and they will be collected from the start of study intervention administration through the end of the intervention.

Any AEs that are also classified as symptoms associated with PASC and collected during the study will not be collected as a safety event to the study database or further assessed by the site or study personnel because they will be collected as part of the PASC symptom dataset.

Serious adverse events (SAEs) will be collected from the first invasive study procedure (blood collection or nasal swab) through the End of Study for all appendices that use a study drug and through the EOI Clinic Visit for all appendices that include other interventions.

UADEs will be collected in the clinical database from the start of the intervention through the end of the intervention.

Adverse events (AEs) that qualify as an ESI, even if a non-serious AE, will be collected from the start of the study intervention through the End of Study (30 ± 3 days after EOI) for all appendices that use a study drug and through the EOI Clinic Visit for all appendices that include non-drug interventions.

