13.4 MODAFINIL INFORMATION

13.4.1 RISK ASSESSMENT

Modafinil is indicated to improve wakefulness in adult patients with excessive sleepiness associated with narcolepsy, OSA, and shift work disorder. Participants taking modafinil have reported serious rash requiring hospitalization and discontinuation of treatment. The most commonly observed AEs (\geq 5%) associated with the use of modafinil in primary disorders of sleep and wakefulness were headache, nausea, nervousness, rhinitis, diarrhea, back pain, anxiety, insomnia, dizziness, and dyspepsia.⁵⁸

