13.4.4 DOSING AND ADMINISTRATION

Modafinil administration will total 10 weeks. Over the first 3 weeks, modafinil will be titrated starting at 100 mg daily in the morning. Specifically, every 5 days (±2 days) the study team will call participants to discuss titration according to the following schedule:

- 1. 100 mg daily in the morning°
- 2. 200 mg daily in the morning°
- 3. 200 mg daily in the morning° and 100 mg in the early afternoon•
- 4. 200 mg daily in the morning° and 200 mg in the early afternoon•

°morning is 11:59 am or earlier

•early afternoon is at least 4 hours after morning dose and at least 8 hours before scheduled bedtime.

Example: A participant with a scheduled bedtime of 11:30 pm would take the early afternoon dose no later than 3:30 pm, which would require taking the morning dose no later than 11:30 am

Following the titration (the last 7 weeks), the minimum dose will be 100 mg in the morning up to a maximum dose of 200 mg in the morning plus 200 mg at noon (total daily dose of 400 mg), depending on the participant's tolerance as assessed by regular phone calls and symptom reports. Placebo dosing will follow the same titration scheme.

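### Non-serious insomnia and decreased appetite that do not stop treatment are not collected as adverse events in Appendix A, although the solriamfetol titration text singles out both

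*Protocol*

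**What the plan says.** **Collection rule (Protocol 9.1.2).** Participants may report non-serious AEs, but these "will not be collected into the study database as an AE or further assessed by the site or study personnel". There are two exceptions. An AE that ends study intervention is entered as the reason for stopping and reported as an AE. An AE that is an ESI is collected even if non-serious, through End of Study for drug appendices. Serious AEs are collected separately. An AE that is also a PASC symptom is not a safety event, because it is expected in the PASC symptom dataset.

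**ESI list (13.6).** "The following ESIs will be collected for Appendix A": hypertension, rhinitis, pharyngitis, headache, rash, diarrhea, nausea/vomiting, back pain and psychiatric event. The last is not defined in the protocol.

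**Solriamfetol (13.5.1, 13.5.4).** Titration proceeds unless a study physician judges adverse reactions likely attributable to treatment, "with special attention to headache, nausea, decreased appetite, insomnia, anxiety, or BP exceeding the threshold described in the study exclusion criteria". It continues: "In the case of adverse reactions, the dose may be reduced to the most recent prior dose at weekly intervals". Section 13.5.1 lists decreased appetite (6% to 7%) and insomnia (0% to 1%) among AEs more frequent than on placebo.

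**Modafinil (13.4.1, 13.4.4).** The AEs at 5% or more are "headache, nausea, nervousness, rhinitis, diarrhea, back pain, anxiety, insomnia, dizziness, and dyspepsia". The dose is set "depending on the participant's tolerance as assessed by regular phone calls and symptom reports", with no event named.

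**The concern.** Because of 9.1.2, the ESI list decides which non-serious tolerability events exist as AE data. Two events that staff are told to watch for during solriamfetol titration are not on it. A site could hold or reduce a dose for either one without any AE entry. Insomnia matters particularly, since the drugs promote wakefulness and the trial concerns sleep. At stake is whether Appendix A can report AE rates by arm, with onset, attribution and action taken, for effects that its own text links to the drugs.

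**Working it through.** The point rests on setting passages side by side; the plan states no figure to reproduce.

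**Step 1. What reaches the safety analysis.** Section 10.4.3 analyses SAEs, ESIs, and AEs or SAEs leading to discontinuation, which are the same routes as in 9.1.2. Section 9.1.3 puts severity, relationship and action taken on the CRF for reportable events.

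**Step 2. The two events against the text.**

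| | Insomnia | Decreased appetite |
|---|---|---|
| On the ESI list (13.6) | No | No |
| Named in solriamfetol titration (13.5.4) | Yes | Yes |
| Solriamfetol risk (13.5.1) | 0% to 1% | 6% to 7% |
| Modafinil risk (13.4.1) | 5% or more | Not named |
| Measured elsewhere | ISI, PROMIS 8b SD, sleep diary, tracker | Weight only, indirectly |

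A severity threshold does not explain the omission, since rhinitis, diarrhea and back pain are on the list. There is also a tension between sections. Under 13.5.4 a study physician judges whether such a reaction is attributable to treatment, while 9.1.2 says a non-serious, non-ESI event is not assessed further.

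**Step 3. Can the efficacy scores stand in?** ISI is taken at Baseline and EOI with a 2-week recall (8.8.2.5). PROMIS 8b SD has a 7-day recall and is repeated at End of Study. Treatment lasts 10 weeks (70 days), and the earliest EOI visit is the first day of the last week (8.5), which is day 64. The ISI then reaches back to about day 64 − 14 = 50, and 8b SD to about day 64 − 7 = 57. Titration calls end at about day 20. Insomnia that appears in titration and resolves after a dose change therefore ends about 30 days before either recall window opens. Neither score carries onset, attribution or action taken.

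**Step 4. Scale, on assumptions.** The planned active arm is 237 (13.7.1). The share *s* on solriamfetol is not given, so it is assumed.

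- Decreased appetite on solriamfetol = 237 × *s* × (0.06 to 0.07).
- Insomnia on solriamfetol = 237 × *s* × (0 to 0.01).
- Insomnia on modafinil, at least 237 × (1 − *s*) × 0.05.

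| Assumed *s* | Appetite | Insomnia, solriamfetol | Insomnia, modafinil (at least) |
|---|---|---|---|
| 10% | 1.4 to 1.7 | 0 to 0.2 | 10.7 |
| 25% | 3.6 to 4.1 | 0 to 0.6 | 8.9 |
| 50% | 7.1 to 8.3 | 0 to 1.2 | 5.9 |

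These are expected occurrences, not unrecorded cases: any that are serious or stop treatment would be captured. Section 13.5.1 does not make clear whether its percentages are rates or excesses over placebo.

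**The case against.** The strongest reply is that 13.5.4 governs dosing decisions and 13.6 governs what enters the database. Watching for an event without making it an ESI is then selective safety collection rather than an error. Insomnia is also heavily measured, with a randomised comparison of ISI and PROMIS 8b SD, plus diary and tracker data. Tracker wear during treatment is encouraged, though optional, and PGIC is scheduled within the intervention period. Section 9.1.2 may route insomnia to the PASC symptom dataset on purpose, since section 2.2 describes insomnia as part of PASC.

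Much of this stands, and it limits the point. A reader might infer four stronger claims that the protocol does not support:

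- *The events are never recorded.* Serious cases and those that stop treatment are recorded, and insomnia severity is measured in both arms. Whether the PASC Symptom Questionnaire covers appetite is not stated.
- *These are the commonest drug-attributable complaints.* Solriamfetol insomnia is put at 0% to 1%. Headache, with the highest upper figure in 13.5.1, is already an ESI. The modafinil figure is an observed frequency, not an excess over placebo.
- *Both drugs tie dosing to these events.* Only the solriamfetol text names them.
- *The DSMB will not see them, and dose reductions will have no recorded reason.* These depend on the DSMB Charter and the Manual of Procedures, which are not shown.

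The objection does not remove the gap. Efficacy scores at two or three time points are not AE records, and an event that staff may act on during titration is, by 9.1.2, not one to assess further. The list in 13.6 is disordered in the available text, but no fragment suggests a lost entry for either event.

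**Conclusion.** The concern holds in limited form. Non-serious insomnia and decreased appetite that only hold or reduce a dose are not collected as AEs in Appendix A, and 9.1.2, 13.5.4 and 13.6 need to be reconciled. Decreased appetite is the clearer gap, because no direct measure of it is shown. For insomnia, what is missing is onset, attribution and action taken, and the case there rests mainly on modafinil's 5% or more. The counts above are illustrative only, since they depend on an assumed drug split. The primary efficacy analysis is unaffected. This is a worthwhile, inexpensive improvement to the safety data rather than a flaw that invalidates the safety comparison.

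**What to change.** Add insomnia and decreased appetite to the ESI list in 13.6, and capture them at the existing titration calls and the 42-day call. Section 8.4.2 already requires a safety assessment at each contact during the intervention, so no new contact is needed.

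Two clarifications should go with this. First, state that these ESIs are collected despite the 9.1.2 exclusion of AEs that are also PASC symptoms; otherwise two instructions compete for insomnia. Second, state what psychiatric event covers, for example whether it includes anxiety.

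Dizziness and dyspepsia, both in 13.4.1, are optional additions: no dosing text names them, so the mismatch between sections does not extend to them.

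The cost is two more items on the ESI form and a little extra data entry per case. No dosing rule changes.

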13.7 STATISTICAL CONSIDERATIONS (APPENDIX LEVEL)

13.7.1 SAMPLE SIZE DETERMINATION

An Analysis of Covariance (ANCOVA) linear regression model will be used to compare PROMIS-8a Tscores for the investigational intervention versus control at post-treatment measurement with an

adjustment for the baseline PROMIS-8a measurement. The key determinants of power include the number of participants (ie, sample size), the hypothesized difference in mean T-scores at follow-up for investigational intervention versus control among participants with similar baseline T-scores (ie, the treatment effect), and the standard error of the regression coefficient representing the mean difference in the ANCOVA model. A clinically meaningful treatment effect is assumed to be 5 T-score. The amount of statistical information about treatment effect (β_{trt}) can be quantified as $I = [Var(\hat{\beta}_{trt})]^{-1}$ which is the reciprocal of the estimated treatment effect variance in the primary analysis ANCOVA model. In order to detect a treatment effect of ($\beta_{trt} = 5$) with power $1 - \beta$ and two-sided type-I error α , the required amount of statistical information is given by I = { $(z_{\alpha/2} + z_{\beta})/5$ }² where $z_{\alpha/2}$ and z_{β} are the $(1 - \alpha/2)$ and $(1 - \beta)$ quantiles of the standard normal distribution. The sample size estimation is based on the rough approximation of $V(\hat{\beta}_{trt}) \approx \frac{4\sigma^2(1-R^2)}{n} \cong \frac{4\sigma^2}{n}$, when $R^2 \approx 0$, here σ^2 is the variance of PROMIS-8a T-scores within each treatment group, R^2 is the ANCOVA model's coefficient of determination, and n is the total sample size for active intervention plus control. If the estimated treatment effect is assumed to be 5 units, $\hat{\sigma} = 15$ units (ie, an effect size of .33), two-sided type I error of .05, thus the required total sample size for 90% power to detect a treatment effect of 5 T-score units is 379 participants. Accounting for a 20% attrition rate will lead to a total sample size of 474 participants, which is 237 participants per group (Figure 4).

Standard deviation

Figure 4. Sample Size Estimates Using the ANCOVA Model

14 APPENDIX B: COMPLEX PASC-RELATED SLEEP DISTURBANCES (CPSD)

14.1 STUDY DESIGN AND RATIONALE

The Complex PASC-Related Sleep Disturbances (CPSD) Appendix B combines brief education and a tailored sleep timing prescription for CPSD (referred to as RESET-PASC) with therapies that modify circadian timing for participants who report poor sleep quality or daytime sleep-related impairment. The intervention therapies involve tailored lighting (TL) and melatonin. Participants will be randomly assigned to one of four groups: (a) active TL + oral melatonin, (b) active TL + placebo melatonin, (c) placebo TL + oral melatonin, and (d) placebo TL + placebo melatonin. All groups will receive RESET-PASC. The 2x2 factorial design schema is shown in Figure 5. The intervention duration will be 9 weeks.

Figure 5. Appendix B 2x2 Factorial Design

		Pharmacologic Intervention						
_		Melatonin	Placebo					
imenta ention	Light	Melatonin + Light	Placebo + Light					
Environmental Intervention	Placebo Light	Melatonin + Placebo light	Placebo + Placebo light					
_	Reset-PASC							

PASC can lead to complex sleep disturbances that present similarly to but have overlapping qualities of known types of disturbed sleep, such as insomnia and circadian rhythm/sleep-wake disorders. Both types of sleep disturbances affect one's ability to sleep at night, and many patients with PASC present with symptoms of both insomnia and sleep-wake rhythm disturbances, suggesting common underlying mechanisms. Intervention strategies for the two conditions often overlap. Thus, the interventions in this study target common underlying mechanisms and represent the typical, real-world approaches for treating patients with complex sleep disturbances.

Light-dark patterns are the major synchronizers of circadian rhythms to the local light-dark cycle, which influence sleep timing and quality. Insufficient exposure to morning light or exposure to high light levels in the evening or night can lead to circadian disruption, resulting in sleep-wake irregularity, poor sleep quality, poor cognitive performance, higher depressive symptoms, higher stress, and increased fatigue. Light in the built environment, especially at home, can be too low to entrain the circadian system during the day. Lack of entrainment or circadian misalignment may reduce the strength of circadian rhythms, and can also negatively impact immune function and inflammation. Melatonin is a hormone produced during darkness at night. It prompts appropriate nighttime behaviors and physiological functions including, in humans, sleep. Circadian misalignment may dysregulate melatonin production at night. Poor sleep and other symptoms may be improved by optimizing the alignment of a participant's circadian rhythms strengthening and alignment can be accomplished with the administration of appropriately-timed light in the morning and oral melatonin 2 hours before the scheduled bedtime.

1) The RESET-PASC educational component will be delivered by video (and/or paper brochures) and electronic reminders and will include content on optimal sleep habits, the role and use of melatonin and light for sleep, and recommendations on bedtimes (based on information on the sleep diary and the Split Week Sleep Assessment of Sleep (SASS-Y)).

Sleep onset variability, assessed from an activity tracker used for 7 days at Baseline and EOI, is an endpoint for only this appendix. Night to night sleep onset variability is an objective measurement that, when combined with the subjective PROMIS 8b SD, will help characterize the intervention's effect on CPSD. Further, sleep onset variability is a clinically interpretable and meaningful measure as it correlates strongly with overall sleep-wake variability (eg, sleep midpoint variability).

14.1.1 PRIMARY OUTCOME MEASURES AND ENDPOINTS

Primary: PROMIS 8b SD to assess sleep disturbance and activity tracker to assess sleep onset variability

Secondary outcome to the Primary Objective: PROMIS 8a SRI

14.1.2 SCHEDULE OF ADDITIONAL PROCEDURES

The full schedule of procedures from Table 3 is shown for operational ease starting on the next page. Table 3 abbreviations: EOI – End of Intervention; PASC – Post-acute sequelae of SARS-CoV-2 infection; PROMIS – Patient-Reported Outcomes Measurement Information System

Procedures	Pre- randomization Visits	Baseline Visit	Pre- intervention	Intervention		End of Study
Study weeks	Wk-6 to -1	Day 0	Wk 1	Wk 2-8	EOI Clinic Visit ¹⁶ Wk 9	EOI + 30 days
Informed consent, platform	Х					
PROMIS8a SRI and 8b SD	Х	X ¹⁷			Х	Х
Sleep-screening questions	Х					
Demographics	Х					
Concomitant medications	Х	X ¹⁷			Х	
Medical history	X ¹⁸					
Pregnancytest	Х	X17				
Nasal swab	Х	X ¹⁷				
SRBD screening/HSAT ¹⁹	Х					
Appendix-level eligibility criteria	Х					
Informed consent, appendix level	Х					
RANDOMIZATION		Х				
Height (H) and weight (W)		H/W			W	
Sleep Phenotype questionnaire		Х				
PROMIS10a Fatigue		Х			Х	
ECog2		Х			Х	
Neurocognitive Battery		Х			Х	
PASC Symptom Questionnaire		Х			Х	
ISI		Х			Х	
ОНQ		Х			Х	
DSQ-PEM		Х			Х	

Table 3. Schedule of Procedures for Appendix B - Complex PASC-Related Sleep Disturbance

¹⁶ An Early Termination Clinic Visit will be request for participants who prematurely discontinue the study intervention. This visit will mirror the EOI Clinic Visit and obtain as much data as the participants allow. Refer to Section 8.6.

¹⁷ If necessary; see Baseline visit, Section 8.3

¹⁸ At every clinic visit after screening visit, changes in medical history including SARS-CoV-2 infection since last visit will be collected.

¹⁹ Not necessary if participant has had a sleep apnea screening and documented adherence within 6 months of Screening

Procedures	Pre- randomization Visits	Baseline Visit	Pre- intervention	Intervention		End of Study
Study weeks	Wk -6 to -1	Day 0	Wk 1	Wk 2-8	EOI Clinic Visit ¹⁶ Wk 9	EOI + 30 days
PGIS		Х			Х	
PGIC				Х	Х	Х
Blood for Biorepository		Х			Х	
Stool for Biorepository		Х			Х	
Sleep diary		Distribute	Complete ²⁰		Complete ²⁰	
Activity tracker		Distribute	Wear ²⁰	Wear (optional)	Wear ²⁰	Wear ²⁰
RESET-PASC		Session 1		Sessions 2-5		
SASS-Y + light use		Х		Х		
Blinded melatonin		Distribute		Х	Return	
Blinded tailored light		Distribute	Installation ²¹	X ²²	Х	
Blue Iris light sensor		Distribute	Wear ²⁰	Wear (optional)	Wear ²⁰	
Safety assessment		Х		X ^{23,24}	Х	X ²³
Healthcare Encounter survey				X ²⁴	Х	
Pill count/light adherence				X ²⁵	Х	

²³ Phone call only

²⁰ Data to be collected for 7 days. Refer to the MOP for specific timing and duration of data collection.

²¹ Tailored lighting team members will call as needed to assist participants with light sensor use.

²² Tailored lighting team members will call as needed to assist participants with timer set-up.

²⁴ At 30 ±7 days. Other phone calls can occur as necessary; assessed at every patient contact.

²⁵ By phone call; can be combined with the safety assessment.

